Quality Gap: Colonoscopy quality is linked to patient outcomes. The national VA healthcare system has lacked a comprehensive program to measure and report colonoscopy quality and help providers improve adenoma detection.¹⁷ Accurate measurement of quality metrics is challenging because validated quality metrics are not available in structured VA data from VA CDW. The challenge is multifactorial. Colonoscopy procedure documentation resides in text notes in Vista/CPRS or endoscopic reporting software. The commonly used VA endoscopy note writer software programs (i.e. Endopro®, Provation®, etc) do not facilitate tracking of pathology data and quality measurement. [These same issues will persist with the move to Cerner Millennium® over the next decade unless an infrastructure is in place to collate and process colonoscopy quality data.] Thus, within VA, there has not been a reliable, efficient way to measure colonoscopy quality and ensure optimal protection from CRC incidence and death for Veterans.

Proposed Solution and Rationale for Study:

A primary justification for this study is that VA-EQuIP has a high probability of improving a quality metric outcome (ADR) directly associated with CRC death, one of the most common cancers in Veterans. A randomized controlled trial of this magnitude is an opportunity to show, for the first time, that even small improvements in clinical performance from audit and feedback, with support to improve skills and quality, can save Veterans lives, since even a 1% increase in ADR translates to a 3% reduction in interval cancer death. Our proposal for a randomized program evaluation is a tremendous opportunity to determine the large scale effect of the VA-EQuIP strategy on changes in the colonoscopy quality metrics of individual endoscopists over time. The evaluation of VA-EQuIP implementation will identify factors associated with effective implementation and colonoscopy quality improvement at VA sites. Our prior and planned work builds toward our long-term goal to reduce mortality in Veterans by increasing early detection of CRC and inform national quality improvement initiatives such as remediation training for continual low performing endoscopists.

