Secondary impacts of proposed research: The reported quality metrics could potentially contribute to ongoing professional practice evaluations (OPPE), which we will evaluate during the trial. Measurement of completeness (i.e. cecal intubation rate) and inspection quality (i.e. ADR) of colonoscopy is a recommended part of OPPE for VA endoscopists, and emphasizes to VA providers that VA values high quality procedures for Veterans. However, current data limitations and the time burden for manual data collection and processing are major impediments to providing and tracking accurate performance data to incorporate into OPPEs. **The reporting of quality measures will also improve access to care.** Colonoscopies with poor bowel preparation result in canceled procedures or repeat procedures at earlier intervals (e.g. 1 year). More repeat procedures leads to decreased access to endoscopy specialty care for new patients. If VA could identify and highlight high quality endoscopy centers and endoscopists, that data could be used to promote system wide improvement, protocol and documentation standardization, and adoption of best practices to ensure access to high quality colonoscopy for all Veterans.

Audience for research results and how they will use the products: VA-EQuIP will have multiple primary and downstream users and stakeholders including:

- The VA National Gastroenterology Program Office as noted above, the sponsor of VA-EQuIP.
- The Office of Specialty Care and Primary Care to ensure Veterans are referred to high quality providers.
- The Office of Veterans Access to Care (OVAC) and National GI Access initiative to ensure that access initiatives are aligned on providing Veterans with high quality procedures.

The proposal directly addresses VA priorities by system modernization and efficient use of resources.

1. “Modernize our systems”: National standardized colonoscopy quality reporting will improve infrastructure and streamline services by providing accurate, prospective quality monitoring that currently does not exist.
2. Focus resources more efficiently: The manual chart review used by most sites to capture quality metrics results in significant unaccounted work burden across the VA healthcare system. VA EQuIP will make this inefficient practice obsolete.

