We created an operational database of colonoscopy procedures and linked pathology notes housed in the VA CDW Text Integration Utility that can be semi-automatically updated with the most current data across the VA healthcare system. We have optimized a machine learning document classifier that uses the support vector machine algorithm to delineate a note as either a colonoscopy procedure note, or not. Our process allows to rapidly and prospectively confirm colonoscopy notes for NLP processing and colonoscopy quality reporting. Our NLP pipelines to extract colonoscopy procedure and pathology data have excellent performance (Table 1). The VA-EQuIP dashboard visually presents biannual and cumulative colonoscopy quality metrics to VA sites and providers, and provides comparison metric data at the local site and national level (Figure 2). All reports are created using Microsoft™ SQL Server Reporting Services 2013 and are hosted on a Microsoft SharePoint 2013 internal website. Access is controlled by both SharePoint memberships and local data access permissions.

Usability and [Pilot] Testing: In cooperation with our operations sponsor and partner, we obtained feedback and usability information on VA-EQuIP from the GI Field Advisory Committee. The committee members were provided access to their sites and individual data on colonoscopy quality. Respondents (N=5) provided feedback for internal consistency and were surveyed via the System Usability Scale (SUS).⁴⁹ The average SUS score for VA-EQuIP for 5 respondents was 87.0 (SD 9.9, range 77.5-100). A score >80.3 has been found to be in the top 10% of usability performance based on an ev

Table 1: NLP Performance for Colonoscopy Quality Metrics

Variable	PPV	Sensitivity	F Measure
ADR	98%	100%	99%
Screening Indication	89%	100%	94%
Cecal Intubation Rate	98%	99%	99%
Bowel Prep Adequate	100%	100%	100%

ates for NLP processing and colonoscopy quality reporting. and pathology data have excellent performance (**Table**

Facility Name:North Hospital **Provider Name:** Dr. C **Report Year:** 2017

[figure not shown]

Figure 2: VA-EQuIP Quality Dashboard

RESEARCH OVERLAP

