Colonoscopy quality report card & reporting infrastructure: The VA-EQuIP quality reporting infrastructure includes 2 separate CDW databases with an extract, transform, loading (ETL) framework and secure SharePoint Site to visually present quarterly colonoscopy quality metrics (**Figure 2**). VA-EQuIP has been pilot tested and undergone iterative usability testing with the Gastroenterology Field Advisory Committee.

Data measures: CDW structured data include patient demographics and endoscopist name and specialty (e.g. gastroenterology, surgery). Variables derived from natural language processing of colonoscopy procedure and pathology notes include extent of exam, screening indication, and adenoma detection.

Outcome measures: The primary outcomes are overall and screening ADR for endoscopists after implementation of the quality report cards, [with an average follow up of 19.5 months (range 12-27 months).] Overall ADR is defined as the percentage of patients undergoing colonoscopy for any indication with one or more adenomas detected. Screening ADR is defined as the percentage of patients ≥ 50 years undergoing screening colonoscopy who have one or more adenomas detected. We will assess secondary outcomes measures, including cecal intubation rate and bowel preparation quality. Cecal intubation is defined as passage of the colonoscopy tip to a point proximal to the ileocecal valve so that the entire cecum is visible. The cecal intubation rate is the proportion of colonoscopies with cecal intubation documented in the procedure note. Bowel preparation quality is determined by the endoscopist for bowel cleanliness allowing polyp visualization and removal.

Primary Analysis -- Stepped Wedge at the Provider Level: We will utilize patient data aggregated to the provider level at monthly intervals to examine how the ADR changes pre- and post-intervention. A provider's monthly ADR is the ratio of the total number of the provider's positive ADR screening results to the total number of patients that the provider screened during the month. Prospective data collection will begin Jan 1st, 2020 and conclude Jun 30, 2022, a 30-month data collection period. Baseline data from 2019 will be included in our analysis to augment the pre-intervention time frame, to enable our intervention to start immediately. ADR

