For Aim 1, we have accounted for provider attrition and problematic data in our power calculation, based on our own and historical data provided by the national GI program office. The centralized infrastructure and NLP pipelines of VA-EQuIP will allow creation of reports for all providers in our database to ensure that the NLP system performance remains high throughout the project, several internal validation studies are planned. Each validation will involve a manual annotation of a random set of notes selected at each of the participating sites to create a reference standard. The system performance metrics will be calculated by comparing NLP system output and the reference standard. Since the NLP system was extensively evaluated during development, validation will be limited to measuring precision of extraction. If precision of extraction of each of the variable stays above 90%, the NLP system will be applied on the colonoscopy reports without changes. If evaluation detects decreased precision, detailed error analysis will be performed and system adaptation might be required. If system adaptation is performed, another round of validation will be required. In this case, both precision and recall will be evaluated. Colonoscopies performed on Veterans by providers outside of VA could be assessed for quality metrics using the NLP system contingent on the future integration of the colonoscopy and pathology data into VA CDW.

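### Screening ADR rests on an NLP screening label, and the planned validation cannot rule out a shift in that label when a wave crosses over

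*Combined protocol and SAP*

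**What the plan says.** Aim 1, Outcome measures, defines two primary outcomes. For one: "Screening ADR is defined as the percentage of patients ≥ 50 years undergoing screening colonoscopy who have one or more adenomas detected". For the other: "Overall ADR is defined as the percentage of patients undergoing colonoscopy for any indication with one or more adenomas detected". Only the first needs an indication for each exam.

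That indication is extracted by NLP (Aim 1, Data measures): "Variables derived from natural language processing of colonoscopy procedure and pathology notes include extent of exam, screening indication, and adenoma detection". The source is free text. The Quality Gap paragraph of the Background says: "Colonoscopy procedure documentation resides in text notes in Vista/CPRS or endoscopic reporting software". Table 1 reports PPV 89% and sensitivity 100% for screening indication, the lowest PPV of its four variables.

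The Primary Analysis section enters the log of total screens as an offset, so the denominator is treated as known. The model has categorical quarter effects, baseline covariates, and random effects for site and provider. It has no term for indication mix.

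The pitfalls part of Sample Recruitment plans several internal NLP validations during the project. Each annotates a "random set of notes selected at each of the participating sites". Routine validation measures precision only. The system is used unchanged while precision stays above 90%. A fall leads to error analysis and possibly adaptation, after which recall is measured as well.

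**The concern.** Membership of the screening denominator is decided after randomization, from a note written after the provider knows whether ADR is being fed back. The label could then change with exposure in two ways. A provider might describe borderline exams (screening, surveillance, diagnostic) differently once ADR is on a dashboard. Or the wording of notes might change, so that the NLP reads the same indication more or less accurately.

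A shift common to all sites in a quarter is absorbed by the quarter effects. A shift that begins as each wave crosses over has the same time pattern as the intervention indicator and goes into its rate ratio. At stake is whether a change in screening ADR of the planned size can be read as a change in detection.

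**Working it through.** **1. The plan's own power figure.** Inputs from the Aim 1 Power Calculation: 6 waves of 95 providers, 59 patients per provider per quarter, ICC 0.030, ADR 27.5% rising to 28.5%, one baseline quarter. I added a two-sided 5% level (not stated), six rollout quarters, four follow-up quarters, and rollout quarters counted as treated. Standard stepped wedge generalized least squares gives SE 0.289 points and power Φ(1.0/0.289 − 1.96) = 93.4%, against about 93% stated. If the rollout quarter is dropped, as the design says, the same model gives SE 0.351 and 81%.

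A label artefact is as detectable as a true effect. With no change in detection, the 93.4% model calls a 0.5-point artefact significant 41% of the time and a 1.0-point artefact 93% of the time. Those figures treat all 59 exams as screening. The screening share is not given. At an assumed 30–50%, the figures are 16–24% and 49–70%.

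**2. A changed indication.** Let p = 27.5% (the only baseline ADR given), r the fraction of adenoma-negative exams losing the label, and q the fraction of positives losing it:

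ADR′ = p(1−q) / [p(1−q) + (1−p)(1−r)]

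| r | q | ADR′ | Shift (points) |
|---|---|---|---|
| 2% | 0 | 27.90% | +0.40 |
| 5% | 0 | 28.53% | +1.03 |
| 5% | 2.5% | 28.02% | +0.52 |
| 5% | 5% | 27.50% | 0 |

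An exact 1.0-point shift with q = 0 needs r = (1 − 27.5/28.5)/0.725 = 4.8%. That is 3.5% of the denominator, or 2.07 of 59 exams per provider-quarter (0.62–1.04 at a 30–50% share). All rates here are assumptions, and reversing the direction reverses the sign.

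**3. A changed NLP error rate.** The observed ADR is PPV × A_s + (1 − PPV) × A_n, where A_s and A_n are the ADRs of true screening and of mislabelled exams. A change in PPV shifts it by ΔPPV × (A_s − A_n). If PPV moved from 89% to 95–98% and the gap were 10 points (assumed; range 5–15), the shift would be 0.6–0.9 points (range 0.3–1.35), up or down with the sign of the gap.

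**4. What the planned validation can see.**

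| Change at crossover | Routine validation |
|---|---|
| Endoscopist writes a different indication | Not seen: annotator and NLP read the same text and agree |
| Wording change that lowers recall | Not seen: precision only |
| Wording change that lowers precision to 90% or below | Can be seen, but not tied to exposure |
| Precision moving within 90–100% | No action |

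**5. Power of a check on the labelled share.** Using the same method with 69 sites, 135,517 exams a year, ICC 0.03, four baseline and four follow-up quarters, and the rollout quarter dropped. The expected change in share is share × 0.725 × r.

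| Share (assumed) | SE (points) | r = 5%: change, power | r = 2%: change, power |
|---|---|---|---|
| 0.3 | 0.34 | 1.09, 89% | 0.44, 25% |
| 0.4 | 0.36 | 1.45, 98% | 0.58, 36% |
| 0.5 | 0.37 | 1.81, over 99% | 0.73, 50% |

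The ICC is the plan's figure for patient outcomes. The documents give none for indication mix. The exam count is for all ages.

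Offsetting moves escape this check. If positives equal to 1% of the denominator gain the label and negatives equal to 1% lose it, the share is unchanged and ADR goes from 27.5% to 28.5%.

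**The case against.** The best answer is that the safeguard already exists. Overall ADR is a primary outcome and does not use the label, so a pure labelling artefact would appear as a screening gain with no overall gain, in two results the plan will report anyway. This stands and limits the harm. What is missing is a statement, made in advance, of how discordant results will be read.

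A reader might infer that nothing tests the label. That is too strong. Validations are planned at every site throughout the project. Table 1's 89% already lies below the 90% line, so the plan's own rule could lead to error analysis, adaptation and a recall check. The gap is narrower: the validation is not split by exposure and cannot see a changed indication.

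A reader might also infer that the plan expects notes to be standardized at rollout, because the Significance section mentions "protocol and documentation standardization, and adoption of best practices". That sentence is conditional and speaks of system-wide improvement. The intervention content in the Table 2 implementation strategy covers bowel preparation, polyp identification, technique and improvement cycles, not documentation of indication. A system-wide change would largely fall into the quarter effects.

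Finally, the 1.03-point figure is an extreme case, since it relabels negatives only. Relabelling unrelated to the finding needs far more movement: about 10% of the denominator for 1.0 point at an assumed 10-point ADR gap. That also stands.

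**Conclusion.** The concern holds in limited form. The screening denominator is a post-randomization NLP label with 89% PPV, the model takes it as known, and the planned validation cannot rule out a shift starting at crossover. Such a shift would enter the screening ADR rate ratio.

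The documents do not show that a shift will occur, and its direction is open. A shift as large as the 1.0-point target requires about 5% of negatives and no positives to lose the label; half that rate among positives brings it to about 0.5 points. These sizes rest on assumed relabelling rates, an assumed screening share, and 27.5% serving as the screening baseline. That the audited endoscopists write the notes is implied, not stated.

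It would be wrong to conclude that the screening result is biased, or that a stable labelled share would clear it. With overall ADR already primary, this is a cheap improvement rather than a flaw in the design.

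**What to change.** 1. State in advance that overall ADR is the main check on the label: a screening ADR gain without a compatible overall ADR gain will not be attributed to better detection. Judge compatibility on the confidence interval. With four baseline and four follow-up quarters and the rollout quarter dropped, the SE for overall ADR is about 0.34 points, a half-width of 1.96 × 0.337 = 0.66, so lack of significance alone is not discordance.
2. Fit the same stepped wedge model with labelled screening (yes/no) as the outcome among colonoscopies in patients aged 50 or over. Report its rate ratio and CI beside screening ADR as a sensitivity analysis. State its limits: good power for about 5% relabelling, only 25–50% for 2%, and blind to offsetting moves.
3. Draw the validation notes already planned from both control and intervention months of the same calendar quarters. Report screening-label precision, and recall where feasible, by exposure status. This detects NLP error driven by wording, not a changed indication.

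The cost is one more run of an existing model, a sampling rule for annotation already planned (with some extra annotation if recall is added), and a sentence on interpretation. The downside is that a genuine change in referral mix would also move the labelled share and make the screening result harder to read.

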[Analysis Overview: Our goal is to compare the efficacy of VA-EQuIP versus usual care for the primary outcomes of overall (all indications) and screening indication ADR and secondary outcomes of bowel preparation quality and cecal intubation rate. We hypothesize that VA-EQuIP will lead to a higher rate of ADR, bowel preparation quality and cecal intubation relative to standard of care. We also hypothesize the effect will be particularly pronounced among providers who have low ADR, bowel preparation quality and cecal intubation rates prior to our intervention. The primary analysis takes advantage of the stepped wedge design by simultaneously comparing pre- and post- intervention data both within and across providers to evaluate the effect of the intervention while controlling for secular trends, which are uniform across sites. As a secondary analysis, we will implement a two-stage interrupted time-series and meta-regression analysis, which is commonly used to study intervention effects when an intervention occurs at different times within different providers. For all analyses, our primary inferences evaluate the ratio of ADR with versus without intervention for a given provider. However, our planned analyses also address the data structure, which nests patients within providers within sites.]

Eligibility / Inclusion criteria: We have identified 73 VA sites spanning VA (**Figure 4**) eligible for the study that have endoscopists with colonoscopy procedure and pathology notes in our database (SCS_Endoqual). In 2017, these 73 sites had 657 providers performing 155,926 colonoscopy procedures. The point of contact (i.e. GI section chief) at each site will be contacted by email about planned VA-EQuIP implementation and given specific instructions for accessing site data.

Exclusion criteria: VA facilities without existing colonoscopy procedure or pathology notes in our operational database will not be included in the study.

Consent: The national GI program office will implement VA-EQuIP as an operational initiative. We will obtain provider verbal consent by telephone, if deemed necessary by the IRB, for the evaluation.

Figure 4: VA-EQuIP sites

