We will construct a mixed effects generalized linear model that will act on data aggregated monthly within each provider to estimate the average intervention effect across providers. We will use a Poisson outcome model with a log link to characterize each provider’s monthly rate, where the number of positive screens will be the outcome and the log of the number of total screens will be included as an offset term.^{53,54} In the case of over-dispersion, we will use a negative binomial outcome model. The main predictor of interest will be a pre/post indicator for whether the report card intervention was in effect at a particular month (Intervention). We will additionally control for time since the study began in quarters (Time, coded as a categorical variable) to account for secular trends; as well as site level characteristics obtained from administrative and the quantitative survey data (Aim 1) (urban/rural, cumulative annual procedure volume in 2018 and current volume, site annual ADRs in 2018, use of split dose bowel preparation protocols (SDBP) in 2018, and whether or not ADR was measured in 2018), provider level characteristics (baseline years in practice, primary practice type {academic, hospital employed, private practice}, and baseline annual procedure volume), and baseline patient characteristics aggregated to the provider level (age, sex, race/ethnicity). Since study time will be coded in quarters, it will incorporate seasonal effects in addition to secular trends over the study period. Random effects will be included for both provider and site, where provider is nested within site. Let $PositiveScreens_{ijt}$ denote the observed number of positive screens for the j th provider at site i during month t , and let $TotalScreens_{ijt}$ denote the total number of patients screened. Because the monthly screening rates are expected to be relatively low (≤ 0.30), we assume that the observed number of positive screens, $PositiveScreens_{ijt}$ follows a Poisson distribution with conditional mean λ_{ijt} . We anticipate the following model for λ_{ijt} on a log scale, where $TotalScreens_{ijt}$ is included as an offset term on the right hand side of the equation: $\text{Log}(\lambda_{ijt}) = \beta_0 + \beta_1 Intervention_{ijt} + \beta_2 Time_{ijt} + \beta_3 Urban_i + \beta_4 SiteVolume_i + \beta_5 YrsPractice_{ij} + \beta_6 PracticeType_{ij} + \beta_7 ProviderVolume_{ij} + \beta_8 Age_{ij} + \beta_9 Sex_{ij} + \beta_{10} Race_{ij} + \beta_{11} Volume2018_i + \beta_{12} ADR2018_i + \beta_{13} SDBP2018_i + \beta_{14} ADRMeasured_i + \alpha_i + \mu_{j(i)}$, where β_0 is the intercept, β_2 is a vector of coefficients for the study quarter as expressed by $Time_{ijt}$, α_i indicates the random effect for site i , $\mu_{j(i)}$ indicates the random effect for provider j within site i . $Volume2018_i$ (high/low), $ADR2018_i$ (high/low) and $ADRMasured_i$ (yes/no) are the indicator variables used in stratifying the baseline randomization of sites to waves. We will also examine whether the intervention effect varies by time since intervention and by provider characteristics by considering these interaction terms in the model. Under the proposed Poisson model and logarithmic link function, exponentiating the results will allow us to report rate ratios (RRs), their 95% confidence intervals (CIs), and p-values from the models. Under the generalized linear mixed model the estimated treatment effect, obtained by exponentiating the estimate of β_1 , represents the ratio of the screening rate after versus before implementing the intervention for a given provider.

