Power Calculation: Our power calculation for the intervention effect comes from a stepped wedge model. Based on 2017 data there were 73 sites with 657 providers performing 155,926 cases per year in our sampling frame. We estimate a 5% loss of site data due to data quality issues. We also estimate a provider attrition rate of 8% from four years of data provided by the national GI program office where attrition rates ranged from 6.9-12%.¹⁵ After accounting for data loss and provider attrition, we expect 69 sites with 571 providers seeing 135,517 patients/year, corresponding to 95 providers/wave and 59 patients/provider/quarter. Note that the number of patients seen by providers factors into our power calculation as it affects the standard errors of the intervention effect, where seeing more patients yields greater power. Our primary outcome is ADR, which we will conservatively estimate as having a range of 13-79% based on prior research^{7,8} and our preliminary data. For cluster randomized trials using implementation designs such as ours, the intra-cluster correlation coefficient (ICC) estimates for patient outcomes are approximately 0.030.⁵⁸ Based on an ADR of 27.5% in the pre-intervention period, we would have about 93% power to detect a 1.0% absolute increase in ADR. This difference is clinically important, because a 1% increase in ADR is associated with a 3.0% decrease in risk of incident CRC, and a 5% decrease in risk of fatal interval CRC.⁷ Power calculations were conducted in R using the swCRTdesign package, and are conservative due to exclusion of three quarters of baseline data, and because the second level of clustering by provider is not considered.^{59,60}

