The second stage analysis will consist of random effects meta-regression to aggregate the provider intervention effects estimated from the first stage.^{61,62} This model will enable us to estimate the average intervention effect across providers accounting for heterogeneity at both the site and provider level by including random effects for both. We include a random effect for provider because although we have included the majority of the eligible providers in the VA system, we conservatively consider the providers included in our analysis to be a random sample from the full possible set of providers.⁶⁴ Konstantopoulos et al. describe a similar multilevel meta-regression analysis where studies are nested within school districts – here we have providers nested within sites.⁶⁵ Our meta-regression model will adjust for the variables used in the randomization stratification procedure (*Volume2018*, *ADR2018*, and *ADRMeasured*), provider-level variables (baseline years in practice and baseline annual procedure volume), and site level characteristics including [split dose bowel preparation protocols (SDBP) in 2018,] urban/rural and cumulative annual procedure volume.

Power Calculation: Our power calculation for the overall intervention effect is estimated from an ITS model after accounting for 5% data loss at the site level and 8% provider attrition. On average a provider has 19.5 months of data in both the pre-intervention and post-intervention periods. Thus we estimate 386 patients/provider or 220,215 patients seen in each period. Again, the number of patients is included in the power calculation because the number of patients seen by providers greatly affects the power of our design. To estimate power, we simulated ITS data with varying intervention effect sizes adapting code provided by Rozario et al.⁶⁶ Under an ITS model with an autocorrelated error structure, we expect to achieve 96.8% power to detect a 1.25% increase in ADR from a pre-intervention rate of 27.5% (based on 1000 simulations). Power calculations were conducted in SAS v 9.0.

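### Overall and screening ADR are both primary with no rule for testing them together, and neither stated power figure is shown to hold for screening ADR

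*Combined protocol and SAP*

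**What the plan says.** Two places in Aim 1 name two primary outcomes. The Analysis Overview speaks of "primary outcomes of overall (all indications) and screening indication ADR", and Outcome measures repeats it: "The primary outcomes are overall and screening ADR for endoscopists after implementation of the quality report cards". The denominators are nested. Overall ADR counts every patient having a colonoscopy for any reason; screening ADR counts only those aged 50 or over having a screening examination.

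For inference, the Primary Analysis section promises only that "exponentiating the results will allow us to report rate ratios (RRs), their 95% confidence intervals (CIs), and p-values from the models". It gives no significance level, order of testing or success rule.

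The Power Calculation for the primary analysis refers to one primary outcome, called simply ADR. Its volume starts from the eligibility section: "In 2017, these 73 sites had 657 providers performing 155,926 colonoscopy procedures". After data loss and attrition, "we expect 69 sites with 571 providers seeing 135,517 patients/year". From a 27.5% baseline, "we would have about 93% power to detect a 1.0% absolute increase in ADR". The power section of the secondary interrupted time-series (ITS) analysis says: "Thus we estimate 386 patients/provider or 220,215 patients seen in each period". It claims 96.8% power for a 1.25% increase from the same baseline.

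**The concern.** If one ADR improves significantly and the other does not, the plan does not say whether the trial has succeeded. The headline outcome could then be chosen after the results are seen.

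The two possible rules carry different costs. If either outcome suffices, the chance of a false positive exceeds 5%. If both are needed, error is controlled, but the chance of success is capped by the outcome with fewer patients. That is screening ADR, for which the plan gives no volume, no identified baseline rate and no power. A reader who sees two primary outcomes beside a single 93% may take it to cover both.

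**Working it through.** **1. Which volume the power figures use.** Inputs are from the eligibility section and the two Power Calculation sections.

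- Procedures per provider: 155,926 / 657 = 237.33 a year.
- Providers kept: 657 / 73 = 9 per site; 69 sites × 9 × 0.92 = 571.
- Volume kept: 237.33 × 571 = 135,516 (stated 135,517).
- Per provider per quarter: 135,517 / 571 / 4 = 59.3 (stated 59).
- ITS volume: 135,517 × 19.5 / 12 = 220,215, and 220,215 / 571 = 385.7 (stated 220,215 and 386).

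The only reductions are for site data loss and provider attrition. Nothing is removed for indication or age, so both volumes are all-indication.

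**2. Reproducing the 93%.** The plan does not state alpha, sidedness, number of periods or cluster level. I used the Hussey-Hughes stepped-wedge model (random site intercept, fixed quarter effects) with 69 sites in 6 waves, one baseline quarter (the plan says three were left out), 6 step quarters and 4 follow-up quarters. Two-sided 5% is assumed from the 95% intervals.

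- Patients per site-quarter: 135,517 / 4 / 69 = 491.
- Residual variance at the mean rate: 0.28 × 0.72 = 0.2016.
- Between-site variance at ICC 0.03: 0.03 / 0.97 × 0.2016 = 0.00624.
- Power = Φ(0.01 / SE − 1.96). With the implementation quarter kept, SE = 0.00290, so Φ(3.45 − 1.96) = 93.2%.

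This matches the stated figure. However, the Primary Analysis section says that each wave's three-month implementation data will be discarded. With that quarter dropped and all else equal, SE = 0.00353 and power is Φ(2.83 − 1.96) = 81%. With all four baseline quarters restored as well, SE = 0.00338 and power is 84%.

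**3. Screening ADR.** The screening share is not in the documents and is assumed over a range. Baseline, gain and ICC are held at the plan's values; only the patients per site-quarter change.

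**4. Family-wise error if either outcome counts.** For independent tests, 1 − 0.95² = 9.75%. For a nested subset I took the two test statistics as bivariate normal with correlation √share, which is also an assumption.

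| Screening share (assumed) | Patients per site-quarter | Power: quarter kept, 1 baseline quarter | Power: quarter dropped, 1 baseline quarter | Power: quarter dropped, 4 baseline quarters | Family-wise error, either counts |
|---|---|---|---|---|---|
| 100% | 491 | 93% | 81% | 84% | – |
| 90% | 442 | 91% | 77% | 80% | 6.5% |
| 80% | 393 | 87% | 72% | 75% | 7.1% |
| 70% | 344 | 82% | 66% | 70% | 7.6% |
| 50% | 246 | 69% | 52% | 55% | 8.3% |
| 30% | 147 | 47% | 34% | 37% | 8.9% |

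The 96.8% ITS figure comes from simulations whose autocorrelation is not stated. Only its volume could be checked.

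**The case against.** **The two ADRs are strongly correlated, and the sponsor may intend both to succeed.** The correlation is already in the table; it reduces the inflation but does not remove it. A both-must-succeed rule would remove it, but the plan does not state one. A reader might infer that type I error is definitely inflated. The documents do not support that, because inflation depends on an either-counts rule that is not stated either.

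**The plan calls its power conservative because three baseline quarters are left out.** With the implementation quarter kept, restoring them gives about 95% at full volume and 93/89/85/72/50% at the five shares. Discarding the implementation quarter, as planned, more than uses up that margin: full-volume power is 84%.

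**The 93% might already be meant for screening ADR.** The model description calls its numerator and denominator screens, so the 27.5% could be a screening rate. This stands in part. It means the 93% cannot simply be labelled as power for overall ADR, although a reader might infer that from the volume. What can be said is that the volume is all-indication and the rate is not identified.

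**The screening baseline may differ from 27.5%.** It may, and power could then move either way. Hence the comparison holds only at the same baseline and gain.

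A reader might also object that power is given for an absolute gain while "our primary inferences evaluate the ratio of ADR with versus without intervention for a given provider". That is not a defect: 27.5% to 28.5% fixes the ratio at 1.036.

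**Conclusion.** The point holds. There are two primary outcomes and no rule for testing them together. The text available ends in the Project Management Plan, so absence is judged on that text; it includes the Aim 1 analysis and power sections, where such a rule would belong.

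Under an either-counts rule, family-wise error is above 5% and at most 9.75%. The narrower 6.5% to 8.9% depends on the assumed shares and correlation. Neither the 93% nor the 96.8% is shown to hold for screening ADR. At the plan's baseline, gain and ICC, screening power must be lower than the figure for full volume; how much lower depends on a share that the documents do not give.

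A reader might conclude from the table that screening ADR is underpowered. The documents do not support that: the shares are assumed and the screening baseline is unknown. Nor does the table prove how the sponsor obtained 93%, since the layout is inferred. It shows that the layout which matches 93% keeps a quarter that the analysis will discard.

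This should be settled before analysis, but it does not undermine the design.

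**What to change.** Before analysis:

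1. Pre-specify a fixed-sequence test at two-sided 5%, with the order chosen and justified by the sponsor, or state that both outcomes must succeed.
2. State which ADR the 27.5% and the patient volumes in both power sections refer to, and do not present the 93% or the 96.8% as covering both outcomes.
3. Add a separate power figure for screening ADR, using the 2017 count of screening colonoscopies at age 50 or over and the screening baseline rate from the existing database. Compute it with the implementation quarter discarded, as the analysis plans.

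The cost is SAP wording, one count and one rate from data already held, and a power run. Design and data collection do not change. The downside is that a fixed sequence allows no confirmatory claim on the second outcome if the first fails, and the stated screening power may be below 93%.
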